	(2) Health literacy	Short Assessment of Health Literacy (SAHL)	Enrollment	2.5 minutes
	(3) Discrimination	Discrimination Questionnaire	Enrollment	4 minutes

Process measure	(4) Reach Out and Read Receipt	ROR Receipt Questionnaire	Enrollment, 9 m, 18 m	4 minutes
Primary Outcomes	(5) Language skill acquisition	Expressive One-Word Picture Vocabulary Test - Fourth Edition (EOWPVT-4) Spanish-Bilingual - Complete	18 m	5-20 minutes
		MacArthur Bates CDI	Enrollment, 9 m, 18 m	20 minutes
	(6) Social-emotional skill acquisition	Devereux Early Childhood Assessment (DECA)	Enrollment, 9 m, 18 m	5 minutes
	(7) Shared reading (Parent investment) and parent responsiveness	Modified StimQ Read scale	Enrollment, 9 m, 18 m	5 minutes
		StimQ Parental Verbal Responsiveness	9 m, 18 m	6 minutes
		DialogPR Observation of parent-child interactions	9m, 18 m	4 minutes
	(8) Positive and negative parenting behaviors	Parenting Your Infant, Parenting Your Toddler	Enrollment, 9 m, 18 m	4 minutes
		Parent Discipline Questionnaire	Enrollment, 9 m, 18 m	< 1 minute
Secondary outcomes	(9) Reading attitudes and knowledge	Parent Reading Belief Inventory (PRBI)	9 m, 18 m	3 minutes
	(10) Access to community resources	Adapted Survey of Income and Program Participation (SIPP)	Enrollment, 9 m, 18 m	2 minutes
	(11) Parent-clinician relationship	Modified Physician-Parent Communication Survey	Enrollment, 9 m, 18 m	2 minutes
	(12) Parent stress and wellbeing	Adapted LINK survey	Enrollment, 9 m, 18 m	8 minutes
		Parental Stress Scale	Enrollment, 9 m, 18 m	3 minutes
	(13) Child media use	Modified ScreenQ-I/T 2.0 (Infant/Toddler)	Enrollment, 9 m, 18 m	6 minutes

C. Study Duration

Up to 5 years; participants will be involved up to 2 years.

D. Endpoints

Study participation will conclude upon completion of data collection

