6.0 Data Management Plan

6.1 Data Analysis

1. Enrollment: We will recruit 630 parent-child dyads (210 per arm) over a 24-month time period. We expect that 80% of the 630 enrolled parent-child dyads will complete the study, leaving 525 parent-child dyads (175 in each arm).

2. Sample size and power:

630 parent-child dyads (210 per arm) will be sufficient to achieve 80% power to detect a 0.3 standard deviation (SD) difference in the primary endpoints language scores on the EOWPVT-4 and social-emotional skill scores on the DECA at 18 months between (1) ROR + texts and ROR only and (2) ROR + texts + Central Intake and ROR + texts, assuming approximately 20% attrition based on our past work²⁹ and using 0.05 significance level. An effect size of 0.3 SD difference would be clinically meaningful since it would be associated with a detectable difference in later cognitive functioning, based on work from a prospective cohort.³⁰ The proposed sample size will provide 99.9% power to detect a 0.6 SD difference between the community resource arm and ROR only, based on the expected additive effects of the text message and enhanced access to poverty-reducing resources.

3. Analysis:

Distributions of baseline characteristics will be summarized overall as well as by randomization group. We will assess the distribution of outcome data using descriptive statistics to check the assumption of normality for continuous variables. We will estimate mean outcomes for each treatment group as well as mean differences between groups (with confidence intervals). If any continuous outcomes are skewed, we attempt log-transformation or other to stabilize the variance and normalize distributions.

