For aim 1, analysis will follow the intention to treat principle, in which participants are analyzed based on their group assignment, whether or not they receive the strategies for all outcomes. Because of the multiple, potentially highly correlated outcomes, the step-down minP method (a re-sampling approach), will be used to assess the effects of treatment³¹ across outcomes and timepoints within each domain (language development, social-emotional development, and parenting). We will use ANOVAs to evaluate treatment effects on adjusted outcomes. Specifically, for outcomes with more than one post-treatment timepoint and a baseline assessment, we will calculate individual- and baseline-adjusted outcomes from linear models with random individual-specific intercepts (random effect) and treatment and baseline as fixed effects. Then, the adjusted outcome is estimated as the observed outcome minus the best linear unbiased predictor (BLUP) of individual-specific intercept and baseline contribution. For outcomes with one post-treatment timepoint and a baseline assessment, a baseline-adjusted outcome

will be estimated from ANCOVA results as the observed outcome minus the estimated intercept and baseline contribution. The differences in means from ANOVAs focused on these adjusted outcomes will estimate treatment effects. For secondary outcomes, statistical significance will be set at $p < 0.05$ without adjustment for multiple comparisons. For language outcomes, we will adjust for child age and sex in sensitivity analyses.

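### Subtracting each child's BLUP before the ANOVA makes standard errors and confidence intervals too small for DECA and most other repeated outcomes

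*Combined protocol and SAP*

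**What the plan says.** The rule is in the combined protocol and SAP, section 6.1, item 3 (Analysis), for Aim 1. For outcomes with a baseline and more than one follow-up, the first stage uses "linear models with random individual-specific intercepts (random effect) and treatment and baseline as fixed effects". No visit term is listed. In the second stage, "the adjusted outcome is estimated as the observed outcome minus the best linear unbiased predictor (BLUP) of individual-specific intercept and baseline contribution". Then: "The differences in means from ANOVAs focused on these adjusted outcomes will estimate treatment effects". The same item plans "mean differences between groups (with confidence intervals".

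For the language, social-emotional and parenting domains, "the step-down minP method (a re-sampling approach), will be used to assess the effects of" treatment across outcomes and timepoints. The plan does not say what is resampled or whether the first-stage model is refitted each time. "For secondary outcomes, statistical significance will be set at" p < 0.05 with no multiplicity adjustment, and no resampling is named for them.

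Section 6.1, item 2 names "social-emotional skill scores on the DECA at 18 months between" arms as a primary comparison. The Data Points table in section 1.3 B schedules DECA at "Enrollment, 9 m, 18 m", so the rule applies to it. The same schedule holds for the CDI, StimQ Read, the parenting and discipline scales, SIPP, physician-parent communication, LINK, the Parental Stress Scale and ScreenQ. The rule does not reach EOWPVT-4 (18 months only), or StimQ Parental Verbal Responsiveness, DialogPR and PRBI (no baseline).

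**The concern.** Each child belongs to one arm throughout, so an arm difference is a between-child comparison and its sampling error includes the variation between children. Treatment is already a fixed effect in the first-stage model, so the predicted child intercepts average to about zero within each arm. Subtracting them leaves the arm difference, and its true variability over repeated trials, essentially unchanged. It does shrink the spread of scores within arms, which is what the ANOVA uses for its standard error. The result is a correct estimate with a standard error that is too small.

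At stake are the interval for a named primary endpoint, the p-values of secondary outcomes with a baseline, and possibly the p-values in the primary domains, depending on how minP is run.

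**Working it through.** **The plan's own figure.** Two-sided 5% power for a 0.3 SD difference with the stated 175 completers per arm is 80.1%, which reproduces the stated 80%. That calculation uses the full between-child SD, which the planned ANOVA would not use. Twenty percent attrition from 210 leaves 168 per arm (power 78.5%), and 168 is used below. The SE ratios do not depend on this choice.

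**Inputs.** From the documents: three equal arms, visits at 9 and 18 months, 20% attrition, alpha 0.05 (taken as two-sided). Assumed, because the documents give no value: rho, the 9-to-18-month correlation after baseline and arm adjustment, and d, the mean shift between visits. Units are residual SDs after baseline adjustment.

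**Closed form, complete data, no visit shift.**
- Shrinkage factor: lambda = 2·rho/(1 + rho).
- Variance left after subtraction: 1 − lambda = (1 − rho)/(1 + rho).
- SE ratio (ANOVA to true): sqrt[(1 − rho)/(1 + rho)].
- True SE: sqrt(2/168) = 0.109.
- Type I error: 2·[1 − Φ(1.96 × ratio)].

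At rho = 0.3 the ratio is sqrt(0.7/1.3) = 0.734 and the ANOVA SE is 0.080. At rho = 0.5 the ratio is sqrt(0.5/1.5) = 0.577 and the SE is 0.063. The 95% half-widths are 0.157 and 0.123 instead of 0.214. Coverage is about 85% and 74%.

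The closed form was checked by simulation: 168 per arm, baseline slope 0.5, no true effect, REML random-intercept fit, 4,000 trials per setting, arm 2 against arm 1 at 18 months.

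| rho | SE ratio | Type I, formula | Type I, simulated |
|---|---|---|---|
| 0.1 | 0.905 | 0.076 | 0.082 |
| 0.3 | 0.734 | 0.150 | 0.145 |
| 0.5 | 0.577 | 0.258 | 0.269 |
| 0.7 | 0.420 | 0.410 | 0.419 |
| 0.8 | 0.333 | 0.514 | 0.511 |

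The three-arm F-test rejected in 19.6% (rho 0.3) and 38.3% (rho 0.5) of null trials.

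**Unmodelled visit shift.** With no visit term, the fitted child variance becomes rho − d²/4, or zero if that is negative. Then lambda = (rho − d²/4)/[(1 + rho)/2], and the variance left is 1 − lambda·(1 + d²/4). For rho = 0.5 and d = 1: lambda = 0.25/0.75 = 0.333, variance left = 1 − 0.333 × 1.25 = 0.583, ratio = 0.764. Simulated type I error:

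| Shift (SD) | rho 0.3 | rho 0.5 |
|---|---|---|
| 0.5 | 0.121 | 0.225 |
| 1.0 | 0.063 | 0.141 |
| 1.25 | 0.046 | 0.085 |
| 1.5 | 0.045 | 0.052 |

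Adding a visit term but keeping the subtraction restores the full inflation even with a 1.5 SD shift: 0.150 and 0.270.

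**Step-down minP over the two visits** (three-arm F, 199 permutations, 1,800 trials per rho). Family-wise error at rho 0.3 and 0.5 was 25.1% and 45.8% when labels were permuted on fixed adjusted scores, and 5.6% and 4.6% when the model was refitted in every permutation.

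**Comparator.** Baseline-adjusted ANCOVA at 18 months on the same data gave type I error of 4.4% to 5.9% in all settings.

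**The case against.** The strongest objection concerns the confidence intervals. Section 6.1 mentions them before it introduces the adjusted scores and does not say which standard error they use, so tying them to the ANOVA is an inference. It is the natural one, because the ANOVA mean differences are the stated treatment-effect estimates and no other source is named.

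Second, inference in the primary domains goes through minP, and with full refitting the error is controlled. That stands. For those p-values the fault is conditional on an implementation the plan does not state. Only the two permutation schemes were examined, not a bootstrap version.

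Third, the documents fix neither rho nor the visit shift. DECA and the CDI change form with age, and section 1.9 does not say whether raw or age-normed scores are analysed. Raw CDI counts may shift enough between visits to make the error negligible. This limits what can be said about size, but not about direction. An analysis that is valid only because an omitted visit effect drives the fitted child variance to zero is not a sound basis.

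Fourth, the algebra assumes complete visits. With 210 per arm, 10% missing at 9 months and 20% at 18 months, and known variance components, type I error was 13.9% and 23.9% at rho 0.3 and 0.5. That is slightly smaller, but the problem remains.

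Finally, the normal-theory sizes do not carry over to the two discipline questions or the resource-use items. Nor does the plan give any rule for outcomes with two follow-ups and no baseline.

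**Conclusion.** The point holds and must be fixed before analysis. As written, the rule understates the standard error of every arm contrast for outcomes with a baseline and two follow-ups, including DECA at 18 months, whenever the fitted child variance is above zero. The point estimate is not biased in complete data.

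Confidence in the direction is high. The size is conditional: with no visit shift, type I error runs from about 8% to 51% over assumed rho of 0.1 to 0.8. It falls to about 5% with an unmodelled 1.5 SD shift at rho 0.3 or 0.5. Intervals taken from the ANOVA are too narrow under either form of minP, and secondary-outcome p-values have no stated protection. Primary-domain p-values are safe only if the model is refitted in each resample.

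**What to change.** Remove the step that subtracts the BLUP and then runs an ANOVA. Adding a visit term to it is not enough. Take arm contrasts, standard errors, confidence intervals and secondary-outcome p-values from one of two models:

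- a repeated-measures mixed model with baseline, visit, treatment, treatment-by-visit and correlated errors within child; or
- a baseline-adjusted ANCOVA at each visit.

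State that step-down minP permutes arm labels by child and refits the whole model in every resample. State whether raw or age-normed DECA and CDI scores are analysed.

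The cost is SAP wording and some computing time, with no new data. Intervals for the affected outcomes become wider: in the no-shift example, a half-width of 0.214 SD rather than 0.157 (rho 0.3) or 0.123 (rho 0.5).

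### Four primary outcomes have no enrollment score, so neither baseline-adjustment rule reaches them, although related enrollment scores are collected in every arm

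*Combined protocol and SAP*

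**What the plan says.** Section 6.1 (3. Analysis, Aim 1) states "We will use ANOVAs to evaluate treatment effects on adjusted outcomes" and then defines two kinds of adjusted outcome.

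- **Rule 1:** "for outcomes with more than one post-treatment timepoint and a baseline assessment, we will calculate individual- and baseline-adjusted outcomes", using a linear model with a random intercept for each individual and with treatment and baseline as fixed effects.
- **Rule 2:** "For outcomes with one post-treatment timepoint and a baseline assessment, a baseline-adjusted outcome" is estimated by ANCOVA.

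The section gives no rule for an outcome without a baseline assessment. The only other covariates named are child age and sex, for language outcomes, in sensitivity analyses.

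The table in section 1.3 B sets the visits. Among the primary outcomes it lists "StimQ Parental Verbal Responsiveness 9 m, 18 m", so no enrollment score. The line "DialogPR Observation of parent-child interactions" also carries 9 and 18 months only, and section 1.9 confirms that the observation is recorded at those two visits. The EOWPVT-4 is given at 18 months only. The "Modified StimQ Read scale", in the same construct row as the first three, is collected at enrollment and at both follow-ups. So is the CDI, in the same row as the EOWPVT-4.

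**The concern.** The two rules do not fit the schedule. One describes a pattern of visits that no listed outcome has. The pattern that several primary outcomes do have, follow-up scores without a baseline, is not described at all.

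Two things are at stake. The first is precision. A related score taken at enrollment can remove part of the between-child or between-parent variation from the comparison, and the plan already collects such scores in all three arms. The second is pre-specification. The step-down minP procedure runs across all outcomes and timepoints in a domain, so every member needs a defined test statistic. For these outcomes the analyst would have to choose one later.

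The gap is not confined to minor measures. It includes the EOWPVT-4, one of the two endpoints named in the power statement in section 6.1, and the only measure of parenting that does not rest on parent report.

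**Working it through.** **Step 1. Sort the measures.** The 15 outcome measures in the section 1.3 B table (DialogPR and the observation counted separately) were sorted by enrollment score and number of follow-ups.

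| Enrollment score | Follow-ups | Rule in section 6.1 | Primary | Secondary |
|---|---|---|---|---|
| Yes | 9 and 18 months | Rule 1 | CDI, DECA, StimQ Read, Parenting Your Infant/Toddler, Parent Discipline | SIPP, physician-parent communication, LINK, Parental Stress Scale, ScreenQ |
| Yes | One | Rule 2 | none | none |
| No | 9 and 18 months | none | StimQ Parental Verbal Responsiveness, DialogPR, observation | PRBI |
| No | 18 months | none | EOWPVT-4 | none |

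Rule 1 covers ten measures and Rule 2 covers none. Five measures, four of them primary, fall under neither.

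**Step 2. Reproduce the plan's power.** Inputs from section 6.1 are a difference of 0.3 SD, significance level 0.05 (two-sided reproduces the figure) and 175 completers per arm.

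Power = Φ(0.3 × √(n/2) − 1.96)

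- n = 175: 0.3 × √87.5 = 2.806, and Φ(0.846) = 80.1%. The stated 80% reproduces.
- n = 168: 0.3 × √84 = 2.750, and Φ(0.790) = 78.5%.

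Both sizes are shown because 80% of 210 is 168, whereas the stated 175 per arm (525 of 630) is 83.3%.

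**Step 3. Add one baseline covariate.** With correlation r between the enrollment score and the outcome, the residual SD is √(1 − r²).

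Power = Φ(0.3 × √(n/2) / √(1 − r²) − 1.96)

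The documents do not give r, so every value below is an assumption.

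| r | Equivalent gain in dyads, 1/(1 − r²) − 1 | Power, 168 per arm | Power, 175 per arm |
|---|---|---|---|
| 0 | 0% | 78.5% | 80.1% |
| 0.2 | 4% | 80.1% | 81.7% |
| 0.3 | 10% | 82.2% | 83.7% |
| 0.4 | 19% | 85.1% | 86.5% |
| 0.5 | 33% | 88.8% | 90.0% |

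**Step 4. What these figures are not.** They apply to a continuous score at one timepoint, tested at unadjusted two-sided 0.05. The planned tests use step-down minP, three of the four outcomes have two timepoints, and section 6.1 codes the observation by whether expected behaviors occurred. The 0.3 SD power statement was written for the EOWPVT-4 and DECA. The table shows the order of the gain and is not the power of the planned tests.

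**The case against.** **Rule 2 may not be idle.** The CDI and DECA change form with age (section 1.9). Children enrolled at 6 to 12 months are 15 to 21 months old at the first follow-up and 24 to 30 months at the second, so a form-specific outcome could have a single usable follow-up. The plan does not say how forms are combined. It is therefore safe to say that Rule 2 matches no outcome as scheduled, but not that it could never be used. This does not help the four outcomes that have no enrollment score.

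**An unadjusted analysis is not stated.** A reader might infer that these outcomes will be compared by a raw ANOVA. Section 6.1 is silent; for the two-visit measures, a random-intercept model without the baseline term is as natural a reading. What the text supports is that neither rule reaches these outcomes and that no baseline adjustment is planned for them.

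**Nothing is biased.** A reader might infer that the treatment comparisons are invalid. They are not: in a randomized comparison, omitting a baseline covariate costs precision only.

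**The mediation analysis is separate.** Parental verbal responsiveness is also a mediator in H2B, but section 6.1 handles Aim 2 with its own methods. The two rules concern Aim 1.

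**The choice of covariate is a judgment.** The plan treats the home literacy environment and verbal responsiveness as distinct pathways, and Parenting Your Infant is also available at enrollment. Nothing in the documents shows that StimQ Read predicts best. For the CDI, section 1.9 gives a lower age of eight months, so some children will be below that range at enrollment. These points limit the likely gain. They do not remove the reason to name a covariate in advance.

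**The observation has fewer dyads.** Parents may decline recording, in which case the exercise is skipped, so 168 is not its sample size.

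**Conclusion.** The point holds as a gap in pre-specification with a modest, nearly free gain in precision. As scheduled, the one-follow-up rule matches no outcome. The EOWPVT-4, StimQ Parental Verbal Responsiveness, DialogPR and the observation are reached by neither rule.

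The size depends on an unstated correlation. On the illustrative scale at 168 per arm, the gain is under 2 percentage points at r = 0.2 and about 10 points at r = 0.5. It also assumes that the enrollment scores are taken before the family's arm is known, which the order of procedures in section 1.3 suggests but does not state.

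The documents do not support any claim of bias, or the claim that a raw ANOVA has been chosen.

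**What to change.** Replace or extend the one-follow-up rule in section 6.1 with wording such as:

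> For primary outcomes with no enrollment score, the related enrollment score in the same domain is the baseline covariate: StimQ Read for Parental Verbal Responsiveness, DialogPR and the observation; CDI, with child age, for the EOWPVT-4. Outcomes with 9- and 18-month scores use a repeated-measures model with this covariate. The EOWPVT-4 uses ANCOVA. Yes/no observation codes use the matching model for binary or count data.

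The text should also:

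- say that the repeated-measures model gives a treatment contrast at each visit, because the step-down minP procedure works across timepoints;
- give a simple rule for a missing enrollment score;
- state the analysis of the PRBI, a secondary outcome with the same visit pattern.

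The cost is SAP wording, to be settled before outcome data are examined by arm. No visit, instrument or participant time is added. The downside is one degree of freedom per covariate if the correlation is near zero.

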Health literacy of parents will be assessed with the Short Assessment of Health Literacy¹⁴ (SAHL), a validated health literacy assessment with good reliability in both English and Spanish speaking samples. The SAHL includes 18 items and takes approximately 3-4 minutes to complete.

We are including a Discrimination Questionnaire which asks a general question about whether the participant and child have ever been discriminated against because of race or ethnicity.

Process measure:

The Reach Out and Read (ROR) Receipt is a brief questionnaire on whether the primary caregiver and child were exposed to literacy promotion in the healthcare setting. Information of interest includes whether a healthcare professional (e.g. doctor, clinic/office staff) ever provided a children's book to take home, whether books were read to children in the waiting room, and whether a healthcare professional ever talked about reading to the child. If applicable, the survey asks for the frequency of any of these events occurring in the past. Questions are adapted from previous work.

Outcomes: We will use validated measures to assess child outcomes.

Language acquisition will be assessed using the Expressive One-Word Picture Vocabulary Test - Fourth Edition (EOWPVT-4) Spanish-Bilingual - Complete. The EOWPVT-4 (Spanish-Bilingual) is a norm-referenced assessment of how well children aged 2+ can name the objects, actions, or concepts presented in full-color pictures. RAs trained by [name] and [name] will administer this instrument at the 18-month visit.

The MacArthur Bates Communicative Development Inventory (CDI)¹⁶ is a measure developed by Fenson et al. to evaluate communicative skills in infants (between eight and eighteen months) and toddlers (between sixteen and thirty months). The short-form version of the measure consists of different forms for infants and toddlers that specifically assess words that the child only understands, only says, and both understands and says at the time of data collection.

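### The primary EOWPVT-4 test leaves out child age and sex, which the plan already intends to use; moving them into the primary model is a small, nearly free gain in precision

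*Combined protocol and SAP*

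**What the plan says.** All references are to the combined protocol and SAP.

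- **Endpoint.** The power paragraph of section 6.1 names as "primary endpoints language scores on the EOWPVT-4 and social-emotional skill scores on the DECA at 18 months" the outcomes on which the trial is sized.
- **Timing.** Section 1.9 says of the EOWPVT-4 that trained staff "will administer this instrument at the 18-month visit", and the Data Points table in section 1.3 B lists it at 18 months only. Section 1.9 also says it "is a norm-referenced assessment of how well children aged 2+ can name the objects" and other items shown. Children enter at 6 to 12 months (section 4.1 C), so no enrollment score is planned.
- **Main analysis.** For Aim 1, section 6.1 says: "We will use ANOVAs to evaluate treatment effects on adjusted outcomes". It then gives two ways to form an adjusted outcome. One is "for outcomes with more than one post-treatment timepoint and a baseline assessment". The other begins "For outcomes with one post-treatment timepoint and a baseline assessment, a baseline-adjusted outcome". Both need a baseline.
- **Age and sex.** The same paragraph ends: "For language outcomes, we will adjust for child age and sex in sensitivity analyses".
- **Availability.** Date of birth is listed among the identifiers in sections 1.9 and 5.1. The planned sensitivity analysis implies that child sex will be held for all arms.

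**The concern.** An outcome measured once, with no baseline, fits neither rule. The reader must infer that the observed EOWPVT-4 score goes straight into an ANOVA on treatment. Section 6.1 also promises group means and mean differences, which fits that reading.

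Most other primary outcomes have their own enrollment value to absorb between-child variation. The EOWPVT-4 does not, so age and sex are the only covariates that the plan names for it, and they are used where they cannot sharpen the primary test. Children will be about 24 to 30 months old when tested (6 to 12 plus 18). Over that range age may explain part of the variation in a vocabulary score, depending on whether raw or age-normed scores are analysed. Section 6.1 does not say which. What is at stake is precision, not validity.

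**Working it through.** **Inputs from section 6.1:** difference 0.3 SD; significance level 0.05 (two-sided assumed, since sidedness is not stated); 175 completers per arm; 80% power.

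**1. Reproduce the plan's figure, no covariates.** Per-arm n = 2(1.960 + 0.842)²/0.3², just over 174, rounded up to 175. This equals the stated number of completers. At 175 per arm, power is 80.1% by the normal approximation. By the noncentral t it is 79.9%, with df = 2 × 175 − 2 = 348 and noncentrality 0.3 × √(175/2) = 2.806. The stated 80% is therefore the power of an unadjusted comparison, and it is met.

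**2. Effect of covariates.** If age and sex explain a share R² of the outcome variance, the residual SD is √(1 − R²). Then:
- standardised effect: d = 0.3/√(1 − R²)
- 95% CI half-width in SD units: 1.96 × √(2(1 − R²)/175)
- equivalent unadjusted n per arm: 175/(1 − R²)

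**3. R² is not in the documents, so two cases are assumed.**

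*Age-normed scores.* Norming removes most of the age effect and leaves mainly sex. For equal numbers of boys and girls differing by δ within-sex SDs, R² = (δ/2)²/(1 + (δ/2)²). An assumed δ of 0.2 gives 0.01/1.01 = 0.010; δ of 0.4 gives 0.04/1.04 = 0.038. The range used is 0.01 to 0.04.

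*Raw scores, age alone.* For ages spread uniformly over six months and a youngest-to-oldest gap of g SD, R² = g²/12. Assumed gaps of 0.5, 0.75 and 1.0 SD give 0.021, 0.047 and 0.083.

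**4. Results at 175 per arm (noncentral t, alpha 0.05).**

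| Case | R² | Power | CI half-width (SD) | Equivalent n per arm |
|---|---|---|---|---|
| Unadjusted | 0 | 79.9% | 0.210 | 175 |
| Normed, sex, low | 0.01 | 80.3% | 0.208 | 177 |
| Normed, sex, high | 0.04 | 81.5% | 0.205 | 182 |
| Raw, age gap 0.5 SD | 0.021 | 80.7% | 0.207 | 179 |
| Raw, age gap 0.75 SD | 0.047 | 81.8% | 0.205 | 184 |
| Raw, age gap 1.0 SD | 0.083 | 83.2% | 0.201 | 191 |

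Taking two further degrees of freedom for age and sex changes no power figure at one decimal. In the raw-score case sex would add somewhat to the age figures.

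**The case against.** The strongest reply is that this is a choice between two valid analyses. The trial was sized for an unadjusted comparison and meets its target. The age- and sex-adjusted estimate will be produced anyway, so the change amounts to swapping the primary and sensitivity labels. With age-normed scores the gain may be only 0.4 to 1.6 percentage points. It can also be said that the EOWPVT-4 is hardly a gap: the two rules say how to remove a baseline contribution, and with one timepoint and no baseline there is nothing to remove.

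Most of this stands. The unadjusted ANOVA is the natural reading, and the gain is modest. What the reply does not answer is why covariates already chosen for this outcome should be kept out of the test that decides it, when including them costs almost nothing.

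Three stronger readings are tempting, and the documents support none of them:

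- *The primary comparison is biased.* It is not. Treatment is randomised, and leaving out age and sex affects only precision.
- *The trial is underpowered for the EOWPVT-4.* At the stated 175 per arm, unadjusted power is 79.9%, which is the stated 80%. Whether retention will deliver 175, and how step-down minP affects power, are separate questions that this change does not settle.
- *Adjustment would raise power greatly.* That would need a larger R² than the age and sex scenarios above give, and nothing in the documents supports one.

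**Conclusion.** The point holds as a minor precision improvement. The primary EOWPVT-4 analysis, read as an unadjusted ANOVA, is sound and delivers the planned power. Adding child age and sex would raise power at 0.3 SD from 79.9% to between 80.3% and 81.5% if age-normed scores are used, or to between 80.7% and 83.2% from age alone if raw scores are used. The precision gained is that of roughly 2 to 16 extra children per arm (177 − 175 to 191 − 175).

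These figures rest on assumed R² values, uniform ages at entry, a two-sided 0.05 test and 175 completers per arm. The direction of the gain is not in doubt if age or sex predicts vocabulary; its size cannot be fixed from the documents.

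**What to change.** In the Aim 1 analysis paragraph of section 6.1:

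1. Make the primary EOWPVT-4 analysis an ANCOVA with treatment, child age at enrollment (from date of birth) and child sex, and use its treatment test in the step-down minP. Age at enrollment is fixed before treatment starts, so it cannot be affected by arm.
2. Keep the unadjusted ANOVA as the sensitivity analysis for this outcome.

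Two clarifications can be made in the same edit:

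- State whether raw or age-normed EOWPVT-4 scores are analysed.
- State which rule applies to StimQ Parental Verbal Responsiveness and to DialogPR and the parent-child observation. The Data Points table lists these at 9 and 18 months with no enrollment assessment, so neither rule covers them. In particular, say whether the individual-specific intercept is removed.

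The cost is SAP wording and two degrees of freedom, with no new data collection. The change should be made before outcome data are compared by arm.
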